9.1.1. Desensitization Response Rates

Desensitization response rate refers to the proportion of subjects who achieve desensitization as determined by tolerating the dose levels specified in [section 7.4](#) of peanut protein with no more than mild symptoms at the DBPCFC. These subjects are termed responders.

All subjects failing to achieve the definition of responder are termed non-responders.

The desensitization response rates at Exit DBPCFC and their associated 95% confidence intervals using exact Clopper-Pearson confidence intervals will be presented for each group/cohort. Desensitization response rates at the maintenance DBPCFC will be presented similarly for Group 1 subjects who complete the maintenance DBPCFC.

The number and percent of subjects at each dose level for highest tolerated dose will also be summarized at the Exit DBPCFC for each group/cohort and at the maintenance DBPCFC for Group 1.

9.1.2. Maximum Tolerated Dose at Exit DBPCFC

The DBPCFCs are based on a modified Practical Allergy (PRACTALL) dosing regimen as described in the ARC003 protocol (Section 3). ARC004 DBPCFCs will include a single highest dose of 2000 mg, whereas ARC003 included a single highest dose of 1000 mg at Exit. With the exception of the 600 mg and 2000 mg doses, the modified PRACTALL doses are approximately on a logarithmic scale.

Sponsor: Aimmune Therapeutics, Inc.

Protocol: ARC0004

Version: Version 1.0, 10Jul2019

The MTD will be summarized at screening and exit along with fold increase from screening for each group/cohort. Subjects who did not tolerate any dose will be assigned an MTD of 0.3 mg to calculate fold change. Changes from screening to the maintenance DBPCFC will be summarized similarly for Group 1 for subjects who complete the maintenance DBPCFC.

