1.2.2 ARC002

All placebo subjects who completed ARC001 were eligible for rollover into the open-label ARC002 study. Placebo subjects in ARC002 underwent an escalation schedule identical to that for AR101 subjects in the ARC001 protocol. All subjects on AR101 who passed the DBPCFC by tolerating ≥ 443 mg cumulative of peanut protein with no more than mild symptoms were also eligible to enter ARC002.

Group 1 included subjects who completed the placebo arm of ARC001 and consented to enroll in ARC002, crossing over to active treatment using the same dosing regimen used in ARC001, but in open-label fashion. After completion of the buildup phase, Group 1 subjects underwent a DBPCFC (to a maximum single dose of 600 mg of peanut protein, or 1043 mg of cumulative peanut protein). Subjects who did not tolerate the post-low-dose buildup phase DBPCFC at ≥ 443 mg were considered escalation failures and were discontinued from the study for safety considerations. Those subjects who tolerated the DBPCFC at ≥ 443 mg of peanut protein entered an approximately 3-month (12- to 24-week) plateau phase of continued dosing at 300 mg/d. Group 2 subjects completed the active AR101 arm of ARC001 and consented to enroll directly into the 300 mg/d, 3-month plateau phase of ARC002. Following completion of the 3-month plateau phase, subjects underwent a post-plateau phase DBPCFC (to a maximum single dose of 1000 mg of peanut protein, or 2043 mg cumulative).

Based on the total population of 26 Group 1 subjects receiving ≥ 1 dose of AR101, 76.9% of subjects tolerated 300 mg and 65.4% tolerated 600 mg. At the post-plateau DBPCFC in 40 subjects in Groups 1 and 2, 100%, 90%, and 60% of the subjects tolerated a cumulative peanut protein dose of 443 mg, 1043 mg, and 2043 mg, respectively. These findings demonstrate the persistence of desensitization during daily maintenance treatment with AR101 at 300 mg/d, further supporting the primary endpoint selection in the ongoing phase 3 trial ARC003. They also indicate that treatment with AR101 may achieve a maximum tolerated dose of food allergen substantially higher than the dose used for maintenance itself.

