It has been previously observed that AR101 was well tolerated and appeared to reproducibly induce desensitization to peanut when used daily. The goal of ARC004 is to examine whether intermittent dosing of AR101 during extended maintenance can preserve the desensitization gained by daily dosing; and if so, how much daily treatment is advisable before the interval can be adjusted. In the short term, the data gained from this study should provide very practical guidance to assist physicians in determining how to manage short-term dosing interruptions. Longer term, the results will have key implications for designing maintenance therapy regimens in future AR101 development protocols.

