6.3.7 Double-Blind, Placebo-Controlled Food Challenge (Groups 1 and 2)

Group 1 subjects will undergo a Post-Maintenance DBPCFC, to be conducted in the same manner as the ARC003 Exit DBPCFC, but with a top dose of 2000 mg (4043 mg cumulative) peanut protein added, as shown in [Table 4](#).

All subjects in Groups 1 and 2 who complete their dosing regimen will undergo an Exit DBPCFC up to a single highest dose of 2000 mg of peanut protein (4043 mg cumulative), according to [Table 4](#). For subjects who do not tolerate their nondaily dosing regimen and subjects who switch to daily dosing after missing their nondaily dose for > 3 days, the Exit DBPCFC will be omitted before discontinuation from ARC004 and enrollment in ARC008. Subjects should not administer their AR101 dose on the day of the DBPCFC. All DBPCFCs will be conducted and evaluated based on PRACTALL guidelines. Sites will be provided a DBPFCFC manual, as in ARC003.

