3.2. SECONDARY ENDPOINTS

The secondary safety endpoints are as follows:

- Frequency of anaphylactic reaction
- Frequency of use of epinephrine as a rescue medication
- Frequency of AEs leading to withdrawal of AR101
- Frequency of AEs in each treatment regimen leading to discontinuation of extended interval dosing
- Frequency of Gastrointestinal (GI) AEIs
- Occurrence of premature discontinuation of dosing due to chronic/recurrent gastrointestinal (GI) AEs
- Frequency of accidental food allergen exposure
- In subjects with asthma, change in asthma control using the Asthma Control Test (ACT) questionnaire
- Frequency of all above safety endpoints by treatment period

The secondary efficacy endpoints are as follows:

- The proportion of subjects in each regimen tolerating a single dose of 600 mg (≥ 1043 mg cumulative) of peanut protein during their Exit DBPCFC
- The proportion of subjects in each regimen who tolerate a single dose of 300 mg (≥ 443 mg cumulative) of peanut protein during their Exit DBPCFC
- The proportion of subjects in each regimen who tolerate a single dose of 2000 mg (4043 mg cumulative) of peanut protein during their Exit DBPCFC
- Maximum tolerated dose and change from baseline* at the Maintenance DBPCFC** and each Exit DBPCFC
- Maximum severity of symptoms at each challenge dose at the Maintenance DBPCFC** and each Exit DBPCFC

Sponsor: Aimmune Therapeutics, Inc.

Protocol: ARC0004

Version: Version 1.0, 10Jul2019

- Frequency of use of epinephrine as a rescue medication at the Maintenance DBPCFC** and each Exit DBPCFC
- Change in QoL as assessed by the food allergy related quality of life questionnaire (FAQLQ) and the food allergy independent measure (FAIM) questionnaires
- Satisfaction with AR101 treatment as assessed by the TSMQ-9 questionnaire and additional questions
- Changes in peanut-specific (ps) serum immunoglobulin E (IgE) and IgG4 levels
- Changes in peanut skin prick test (SPT) wheal diameter

*Baseline is defined as the Exit DBPCFC from ARC003 for both treatment groups.

**Maintenance DBPCFC is defined only for Group 1.

Sponsor: Aimmune Therapeutics, Inc.

Protocol: ARC0004

Version: Version 1.0, 10Jul2019

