7.3. MAXIMUM TOLERATED DOSE AT DBPCFC

The maximum tolerated dose (MTD) for a DBPCFC is defined as the maximum single dose of peanut protein resulting in no more than mild symptoms and determined to have been tolerated (i.e., the subject did not experience any dose-limiting symptoms). Any symptom requiring treatment is inherently dose-limiting; thus, a dose during a DBPCFC cannot be considered “tolerated” if treatment was deemed necessary by the investigator. The MTD at the ARC003 Exit DBPCFC will be used as the baseline amount of peanut protein tolerated. If a subject is administered non-standard doses at a DBPCFC, the MTD will be considered as the highest standard dose (whether administered or not) that is less than the highest tolerated non-standard dose.

When describing the MTD at the Exit DBPCFC, in terms of the cumulative amount of peanut protein, the 1 mg dose will not be included. Thus, subjects who tolerate all dose levels from 3 mg to 300 mg or 1 mg to 300 mg have a cumulative MTD of 443 mg.

Sponsor: Aimmune Therapeutics, Inc.

Protocol: ARC0004

Version: Version 1.0, 10Jul2019

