7.5. DATA DERIVATIONS AND DEFINITIONS

The following definitions and derivations will be used throughout this study:

- Study day is calculated relative to the first dose date in ARC004 as (assessment date – first dose date + 1) for assessments and visits performed on or after the first dose date, and (assessment date – first dose date) for assessments and visits prior to the first dose date.
- In this follow on study, baseline is defined as the last non-missing value prior to the first dose of study treatment in the study where study product is first received. For Group 1 patients (those previously on placebo in ARC003), baseline is relative to first dose of AR101 in study ARC004. For Group 2 patients (those continuing on AR101 therapy from ARC003), baseline is relative to first dose of AR101 in study ARC003. If no ARC004 data were entered for a Group 1 subject, use the last available ARC003 data prior to first dose of AR101 in ARC004. For food challenge end points, the ARC003 exit food challenge will serve as the baseline for both groups.

Sponsor: Aimmune Therapeutics, Inc.

Protocol: ARC0004

Version: Version 1.0, 10Jul2019

- Change from baseline is calculated as observed value after the first dose – baseline value.
- Group 1 Initial Dose Escalation period is defined as the time period beginning with the date and time of the first dose of study product in clinic and ending with the date of the last dose of study product taken prior to Up-dosing.
- Group 1 Up-dosing period is defined as the time period beginning with the date and time of the first home dose of study product at 3 mg, and ending with the date and time of first in-clinic dose at 300 mg. This period will be, ideally, 22 weeks in duration, but may be extended to a maximum of 40 weeks to accommodate dose reductions and re-escalations, if necessary.
- Group 1 Maintenance period is defined as the time period beginning with the date and time of the first home dose of study product at 300 mg and ending with the date of the last dose of study product taken prior to the maintenance DBPCFC. The maintenance period lasts approximately 24 weeks.

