9. EFFICACY

9.1. ANALYSIS OF EFFICACY SECONDARY ENDPOINTS

To confirm the efficacy of AR101 through reduction in clinical reactivity as measured in a DBPCFC to a cumulative dose of 4043 mg, the Exit food challenge will be summarized by group/cohort (Group 1, Group 2 Cohort 1, Group 2 Cohort 2, Group 2 Cohort 3A, Group 2 Cohort 3B, and Group 2 Cohort 3C). For Group 1, the maintenance DBPCFC will be summarized separately. Non-food-challenge efficacy endpoints also will be summarized by group/cohort (Group 1, Group 2 Cohort 1, Group 2 Cohort 2, Group 2 Cohort 3A, Group 2 Cohort 3B, and Group 2 Cohort 3C). Except where otherwise noted, DBPCFC summaries will be included for the completer population for age group 4-17 years.

The study examines DBPCFC changes from the baseline of study ARC004 (i.e. DBPCFC completed at end of study ARC003) to the end of study ARC004.

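### Measured from the declared ARC003 Exit baseline, Group 2 MTD is capped at 1000 mg before and 2000 mg after, so mean change can overstate gains and understate losses

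*SAP*

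**What the plan says.** The two challenges have different top doses. SAP 9.1.2: "ARC004 DBPCFCs will include a single highest dose of 2000 mg, whereas ARC003 included a single highest dose of 1000 mg at Exit". Protocol 6.3.7 agrees: the Group 1 Post-Maintenance challenge follows the ARC003 Exit procedure, "but with a top dose of 2000 mg (4043 mg cumulative) peanut protein added", and the Exit challenge for both groups runs to the same 2000 mg step.

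The SAP makes the shorter challenge the baseline. Section 3.2: "Baseline is defined as the Exit DBPCFC from ARC003 for both treatment groups". Section 7.3: "The MTD at the ARC003 Exit DBPCFC will be used as the baseline amount of peanut protein tolerated". Section 7.5: "For food challenge end points, the ARC003 exit food challenge will serve as the baseline for both groups". Section 9.1: "The study examines DBPCFC changes from the baseline of study ARC004", which it identifies as the challenge done at the end of ARC003. Section 11 records this as a departure from the protocol, whose section 9.2.2 used the ARC003 Screening challenge. SAP 3.2 lists MTD change from baseline as a secondary efficacy endpoint.

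Section 9.1.2, which specifies the MTD analysis, writes the fold increase as being from *screening* and does not say which challenge that is. It notes the unequal top doses but gives no rule for a baseline MTD at the 1000 mg ceiling, and no other SAP section supplies one.

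**The concern.** Protocol 1.3 states the goal: to find out whether intermittent dosing "can preserve the desensitization gained by daily dosing". For Group 2, within-subject change from ARC003 Exit to ARC004 Exit bears directly on that question.

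A baseline MTD of 1000 mg in Group 2 really means at least 1000 mg. The later challenge can reveal tolerance of 2000 mg that was already present and count it as a gain. A fall from 2000 mg to 1000 mg is counted as no change. Both errors push the result upward, towards preserved or improved. A mean change near zero or above it in a BIW cohort could therefore be reported as maintained desensitization when some subjects had lost ground.

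**Working it through.** **Inputs from the documents**
- Dose ladder (Protocol Table 4): 3, 10, 30, 100, 300, 600, 1000, 2000 mg.
- Ceilings: 1000 mg at ARC003 Exit, 2000 mg at ARC004 Exit (SAP 9.1.2).
- Group 2 entry floor: 443 mg cumulative at ARC003 Exit (Protocol 4.2). On the standard ladder, a Group 2 baseline MTD can only be 300, 600 or 1000 mg.
- Share at the ceiling: not given for Group 2. The only hint is ARC002 (Protocol 1.2.2), where "100%, 90%, and 60% of the subjects tolerated a cumulative peanut protein dose of 443 mg, 1043 mg, and 2043 mg, respectively". That is 40 subjects, both groups combined, after a plateau of about 3 months.
- Share of ceiling subjects able to take 2000 mg: not given.

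**Ladder check.** 3+10+30+100+300+600+1000 = 2043 mg; adding 2000 gives 4043 mg. Both match the documents.

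**One subject.** Recorded MTD is the highest ladder dose tolerated, up to the ceiling of that challenge.

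| True MTD, before to after | True fold | Recorded before to after | Recorded fold |
|---|---|---|---|
| 600 to 600 | 1.0 | 600 to 600 | 1.0 |
| 1000 to 1000 | 1.0 | 1000 to 1000 | 1.0 |
| 2000 to 2000 | 1.0 | 1000 to 2000 | 2.0 |
| 2000 to 1000 | 0.5 | 1000 to 1000 | 1.0 |
| 2000 to 600 | 0.3 | 1000 to 600 | 0.6 |
| 1000 to 600 | 0.6 | 1000 to 600 | 0.6 |

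**A cohort with no true change.** Let p be the share at the 1000 mg ceiling and q the share of those who already tolerate 2000 mg. Then:
- mean change = 1000pq mg
- arithmetic mean fold = 1 + pq
- geometric mean fold = 2^(pq)
- median fold = 1.0 unless pq exceeds 0.5

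Geometric mean fold over assumed ranges:

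| | q = 0.3 | q = 0.5 | q = 0.8 |
|---|---|---|---|
| p = 0.4 | 1.09 | 1.15 | 1.25 |
| p = 0.6 | 1.13 | 1.23 | 1.40 |
| p = 0.8 | 1.18 | 1.32 | 1.56 |

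Here pq runs from 0.12 to 0.64, so the mean change is +120 to +640 mg and the arithmetic mean fold 1.12 to 1.64. Only p = q = 0.8 has pq above 0.5, so the median fold is 1.0 in the other eight cells. If q = 0 there is no false gain.

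**A cohort with a real loss.** Assume true starting MTDs of 300, 600, 1000 and 2000 mg in 10, 30, 30 and 30% of subjects (p = 0.6, q = 0.5), with 30% of each stratum losing one ladder step.
- True mean change: 0.3 x (0.1 x -200 + 0.3 x -300 + 0.3 x -400 + 0.3 x -1000) = 0.3 x -530 = -159 mg; geometric mean fold 0.82.
- Recorded: the 70% of the 2000 mg stratum who do not fall add 0.7 x 0.3 x 1000 = +210 mg. Visible losses are 0.3 x (-20 - 90 - 120) = -69 mg. The total is +141 mg; geometric mean fold 1.00.
- With the ARC004 MTD capped at 1000 mg: -69 mg; geometric mean fold 0.87.

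With 40% losing a step, the recorded geometric mean fold is 0.94 (true 0.76), and the recorded mean is still +88 mg (true -212 mg).

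Under no change, the capped summary gives 0 mg and 1.00-fold for every p and q.

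**The case against.** **The specified table may not use the capped challenge.** SAP 10.6 lists Screening, Maintenance and Exit challenges separately, and the protocol's baseline was ARC003 Screening. If *screening* in 9.1.2 means that challenge, the 1000 mg Exit ceiling does not enter the fold increase. It could equally mean the ARC004 Screening and Baseline Visit, whose challenge is the ARC003 Exit one (Protocol 6.2). This stands as a limit on the point. On the first reading, however, the change endpoint declared in SAP 3.2 and 9.1 has no specified analysis, so 9.1.2 needs editing either way.

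**The gain is conditional.** A reader might infer that Group 2 will necessarily show a gain. The documents do not support that: they give no q, and no p for Group 2. The default statistics in SAP 6.1 include the median, which may not move. Geometric means are specified only for the immunoglobulins (9.1.5), though the arithmetic mean is inflated as well.

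**All Group 2 cohorts share the ceiling.** A reader might infer that nondaily dosing is favoured over daily dosing. That does not follow. Cohort 3A (QD) is randomized alongside 3B and 3C with the same ceiling, so a nondaily deficit could still show side by side. But no formal comparison is planned (SAP 6.4), and Cohorts 1 and 2 were filled in order of entry. The weakness lies in the within-cohort change.

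**Other outputs are sound.** Exit response rates at each dose level with exact intervals (SAP 9.1.1) use no baseline. The failure rule in Protocol 7.8.3 is categorical and already treats 2043 mg as the Group 2 top. Baseline MTD (SAP 8.3) and highest tolerated Exit dose (9.1.1) are each tabulated. All of this stands, but two marginal tables do not show who lost, kept or gained tolerance.

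**Capping has limits.** Capping both groups would discard real Group 1 gains after crossover from placebo, and capping cannot reveal a fall from 2000 to 1000 mg. Both points stand and shape the fix.

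**Conclusion.** The concern holds for Group 2, under the baseline the SAP declares. Change from ARC003 Exit compares an MTD capped at 1000 mg with one that can reach 2000 mg, and the SAP has no rule for this. To the extent that ceiling subjects already tolerated 2000 mg, the mean or geometric-mean change is shifted upward and can offset or understate a true loss.

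The amount is unknown. The 1.09 to 1.56 range rests on assumed p of 0.4-0.8 and q of 0.3-0.8, with the ARC002 figure of 60% as the only anchor, and the masked-loss example rests on an assumed distribution. It would go too far to say that the study's efficacy results as a whole are inflated: Exit proportions are untouched, medians may be, and all analyses are descriptive. The correction is worth making because this change summary is likely to be read as evidence of preserved desensitization.

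**What to change.** In SAP 9.1.2:

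1. Name the reference challenge for MTD change and fold change, and reconcile *screening* with the ARC003 Exit baseline in 3.2, 7.3, 7.5, 9.1 and 11.
2. For Group 2 only, summarize MTD change from ARC003 Exit on the common dose range, with the ARC004 Exit MTD capped at 1000 mg.
3. Add a shift table per cohort, from ARC003 Exit MTD (300, 600, >=1000 mg) to ARC004 Exit MTD (<300, 300, 600, >=1000 mg), with percentages lost, kept and gained.
4. Report tolerance of 2000 mg separately, as an Exit-only proportion with no change-from-baseline claim.
5. Do not cap Group 1.
6. State that losses above 1000 mg cannot be seen in Group 2, because baseline was not tested above that dose.

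The cost is some SAP wording and one table from data already collected. The small downside is that the Group 2 change summary no longer credits gains above 1000 mg; tolerance at that level remains visible in the 2000 mg proportion.

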9 STATISTICAL CONSIDERATIONS

This protocol outlines the major statistical considerations for the ARC004 study. Full details on the statistical methodology to be used in the analysis and data handling for this trial will be described in the statistical analysis plan (SAP) to be developed prior to database lock and statistical analysis.

Data will be summarized using descriptive statistics within treatment group and cohort. No specific hypothesis testing or comparisons between the treatment groups is planned for this study. Details of within group and within cohort comparisons relative to baseline values and exploratory comparisons between cohorts will be described in the SAP.

Descriptive statistics will be presented in the following manner:

- Continuous data (ie, age, body weight, and height) will be summarized descriptively by mean, standard deviation, median, and range.
- Categorical data (ie, sex and race) will be presented as enumerations and percentages.

Data will be summarized by treatment group, cohort, and treatment phase (as defined in [Section 3.1](#)).

Data will be summarized in tables for each treatment group, treatment groups combined, and treatment phase (as defined in [Section 3.1](#)).

Data from ARC003 will be combined with ARC004 and will be used to define baseline, as appropriate. Additional details about combining data and handling varying exposure times will be described in the SAP. Data will be listed for each subject.

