6. GENERAL ASPECTS FOR STATISTICAL ANALYSIS

6.1. STATISTICAL NOTATION AND METHODOLOGY

Unless stated otherwise, the term “descriptive statistics” refers to the number of subjects (n), mean, median, standard deviation, minimum, and maximum for continuous variables and frequencies and percentages for categorical variables.

Unless specified otherwise, the denominator for percentages for categorical data will be based on the number of subjects or observations with non-missing data appropriate for summary purposes. The denominator for percentages for incidence data (such as adverse events) will be based on the number of subjects in the analysis population “at risk”. Select ordinal data may be summarized using both descriptive statistics and counts and percentages of subjects in each category, as appropriate.

Minimum and maximum values will be presented at the precision of the original value, means, medians will be rounded to 1 decimal place greater than the precision of the original value, standard deviations and standard errors will be rounded to 2 decimal places greater than the precision of the original value. Percentages will be rounded to 1 decimal place. Percentages that round down to 0 or up to 100% will be displayed as “<0.1%” and “>99.9%”, respectively. Other statistics (e.g., confidence intervals (CIs)) will be presented using the same general rules outlined above, or assessed for the most appropriate presentation based on the underlying data.

Unless otherwise noted, values reported as greater than or less than some quantifiable limit (e.g., “< 1.0”) will be summarized with the sign suppressed in summary tables and figures, using the numeric value reported. Data will display on subject listings to include the sign.

Summary tables will be presented by group/cohort displayed as Group 1 and Group 2 with Cohort 1, Cohort 2, Cohort 3A, Cohort 3B, and Cohort 3C. For disposition, demographic, and other summaries of baseline and history data, a Total column for both groups combined will be included. For any summaries of events such as adverse events or concomitant medications, event incidences will be summarized in the Safety population separately for the following group/cohort study periods:

- Group 1: IDE and Up-Dosing, all QD Maintenance (including extended maintenance), Overall
- Group 2 Cohort 2: QOD, BIW, and Overall
- Group 2 Cohort 1 (includes QD only)
- Group 2 Cohort 3A (includes QD only)

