9.1.3. Maximum Severity of Symptoms at DBPCFC

Maximum severity of symptoms at the DBPCFC will be summarized at the 2000 mg, 1000 mg, and 600 mg levels. Symptom severity is determined according to the CoFAR scale at 5 levels: 1-Mild, 2-Moderate, 3-Severe, 4-Life Threatening, and 5-Fatal. Analysis is done on 4 levels: 0-None, 1-Mild, 2-Moderate, 3-Severe or higher (severe, life threatening, fatal). Subjects who experience no symptoms will be assigned a severity of 0-None. Symptom severity data is collected at each challenge dose of peanut protein during the DBPCFC (3 mg, 10 mg, 30 mg, 100 mg, 300 mg, 600 mg, 1000 mg, and 2000 mg). The maximum severity of symptoms observed in the DBPCFC at the specified dose (2000 mg, 1000 mg, or 600 mg) or lower will be used for each subject.

The number and percent of subjects will be presented by maximum severity for the specified challenge dose levels at the Exit DBPCFC for each group/cohort and at the maintenance DBPCFC for Group 1 for subjects who complete the maintenance DBPCFC.

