9.1.5. Changes in Peanut-specific IgE, total IgE and peanut-specific IgG₄

Blood samples will be collected to measure ps-IgE, ps-IgG4 levels, and total IgE. Ps-IgE/IgG4 ratio will be calculated, listed by subject, and summarized by visit and group/cohort. Results outside the limits of quantification will be displayed as less than the lower limit of quantification (LLOQ), or greater than the upper limit of quantification (ULOQ), as appropriate. These values will be summarized as either the LLOQ or the ULOQ. If the ps-IgE or ps-IgG4 is outside of the limits of quantification, the ps-IgE/IgG4 ratio will be calculated using the LLOQ or ULOQ as appropriate.

Summary statistics, including geometric means and geometric standard deviations, will be presented by visit and group/cohort, and change from baseline to each visit will also be presented.

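### SAP 9.1.2 names no statistic for MTD fold change; the default arithmetic mean of ratios favours gains, and no within-subject count of lost, kept and gained dose steps is described

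*SAP*

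**What the plan says.** SAP 9.1.2 states: "The MTD will be summarized at screening and exit along with fold increase from screening for each group/cohort". It adds: "Subjects who did not tolerate any dose will be assigned an MTD of 0.3 mg to calculate fold change". It names no statistic for either MTD or its fold increase.

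Two general rules could fill the gap. In SAP 6.1, the term for descriptive statistics "refers to the number of subjects (n), mean, median, standard deviation, minimum, and maximum for continuous variables". Protocol Section 9 says continuous data "will be summarized descriptively by mean, standard deviation, median, and range", with age, weight and height as its examples. A geometric summary is written down only in SAP 9.1.5, for immunoglobulins: "Summary statistics, including geometric means and geometric standard deviations, will be presented by visit and group/cohort". Yet SAP 9.1.2 itself says that, apart from 600 and 2000 mg, "the modified PRACTALL doses are approximately on a logarithmic scale".

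The reference challenge is not stated consistently. SAP 3.2, 7.3, 7.5, 9.1 and 11 take the ARC003 Exit DBPCFC as the food-challenge baseline, and Section 11 declares this a change from the protocol, which used the ARC003 Screening DBPCFC. SAP 9.1.2 says *screening*. Protocol 6.2 lists Part B of the ARC003 Exit DBPCFC among the ARC004 Screening and Baseline procedures, so the word can be read either way.

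**The concern.** Protocol 1.3 asks whether intermittent dosing preserves the desensitization gained on daily dosing. MTD and its change from baseline is a named secondary endpoint (Protocol 9.2.2, SAP 3.2), and fold change is the only within-subject summary of challenge dose that the SAP describes. For a question about preservation, a summary should treat a lost step and a regained step as equal and opposite. An arithmetic mean of ratios does not: halving subtracts 0.5 from a subject's score and doubling adds 1.0. A cohort with a net loss can therefore show a fold change of 1. The median may also stay at 1, because it responds only when enough subjects move in one direction.

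**Working it through.** **Plan's own figures.** The documents give no expected fold change, so there is none to reproduce. The dose list in SAP 9.1.3 ("3 mg, 10 mg, 30 mg, 100 mg, 300 mg, 600 mg, 1000 mg, and 2000 mg") sums to 443, 1043, 2043 and 4043 mg at the 300, 600, 1000 and 2000 mg doses, matching Protocol Table 4. Ratios of adjacent doses are 3.33, 3.0, 3.33, 3.0, 2.0, 1.67 and 2.0.

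**Set-up.** Fold = exit MTD / reference MTD, with the ARC003 Exit DBPCFC as reference. The cohort patterns below are assumptions for illustration; the documents give no distribution of changes.

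**Symmetric movement.** Equal numbers going 600 to 300 mg (0.5) and 300 to 600 mg (2.0) average (0.5 + 2.0)/2 = 1.25 among those who move. The geometric mean is √(0.5 × 2.0) = 1.00.

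**Net loss.** With 70% unchanged, 20% going 600 to 300 mg and 10% going 300 to 600 mg:
- arithmetic mean = 0.7 × 1 + 0.2 × 0.5 + 0.1 × 2 = 1.00
- median = 1.00
- geometric mean = 2^(−0.2 + 0.1) = 2^(−0.1) = 0.93

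At Cohort 2's planned size of 50, a stronger pattern of 20 losing, 10 gaining and 20 unchanged still gives a mean and median of 1.00. The geometric mean is 2^(−10/50) = 0.871.

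**Which steps matter.** If a loss scores l and a gain scores g, the arithmetic mean is 1 when losers per gainer = (g − 1)/(1 − l).

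| Loss | Gain | Losers per gainer at mean 1 |
|---|---|---|
| 1000→600 (0.60) | 300→600 or 1000→2000 (2.0) | 1.0/0.40 = 2.5 |
| 600→300 (0.50) | 300→600 or 1000→2000 (2.0) | 1.0/0.50 = 2.0 |
| 1000→600 (0.60) | 600→1000 (1.67) | 0.667/0.40 = 1.67 |
| 300→100 (0.33) | 300→600 or 1000→2000 (2.0) | 1.0/0.667 = 1.5 |
| 600→300 (0.50) | 600→1000 (1.67) | 0.667/0.50 = 1.33 |
| 300→100 (0.33) | 600→1000 (1.67) | 0.667/0.667 = 1.0 |

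The 1000→2000 gain is possible because ARC003 stopped at 1000 mg and ARC004 adds 2000 mg (SAP 9.1.2). Set against 1000→600 losses with 40% losing, 20% gaining and 40% unchanged, the mean is 0.4 × 0.6 + 0.2 × 2 + 0.4 = 1.04, an apparent gain, while the geometric mean is 0.6^0.4 × 2^0.2 = 0.94.

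**Median condition at 2:1.** With 2k losers, k gainers and u unchanged, the median is 1.0 only if 2k < (3k + u)/2, that is u > k, or more than 25% of the cohort unchanged. At u = k it is 0.75; with nobody unchanged it is 0.5.

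**The 0.3 mg value.** It plays no part in the examples above. With the ARC003 Exit reference it can be a starting value only in Group 1, since Group 2 must have tolerated 443 mg cumulative to enter. As a sensitivity check, take 49 subjects with a fold of 1 and one going from 0.3 to 300 mg (1000-fold). The arithmetic mean is (49 + 1000)/50 = 20.98 and the geometric mean is 1000^(1/50) = 1.15. With 1 mg in place of 0.3 mg these become (49 + 300)/50 = 6.98 and 300^(1/50) = 1.12.

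A pattern closer to Group 1, wholly assumed, is: exit MTD 1000 mg for all, 5% tolerating no dose at reference, and the rest spread equally over 3, 10, 30, 100 and 300 mg (mean fold (333.3 + 100 + 33.3 + 10 + 3.3)/5 = 96). The arithmetic mean is 0.95 × 96 + 0.05 × 3333 = 258 with 0.3 mg and 0.95 × 96 + 0.05 × 1000 = 141 with 1 mg; the geometric means are 41 and 39. With 2% to 10% tolerating no dose, the arithmetic mean changes by a factor of 1.4 to 2.3.

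At the exit challenge the sensitivity reverses. In the 50-subject example, replacing one 600→300 loss by a fall from 1000 to 0.3 mg moves the arithmetic mean only from 1.00 to 0.99 but the geometric mean from 0.871 to 0.751.

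**If *screening* means ARC003 Screening.** Screening MTDs are not given. For an assumed 3 to 100 mg, an exit MTD of 300 to 2000 mg is a 3- to 667-fold increase, so a fold of 1 does not arise in Group 2. In the 50-subject example with a screening MTD of 10 mg, the mean fold falls from 54 at ARC003 exit to 48 at ARC004 exit, while the median stays at 60.

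**The case against.** The strongest reply is that the SAP never says arithmetic mean. SAP 6.1 defines a term that 9.1.2 does not use, and the table layouts sit in a separate shell document. That stands as a limit: the arithmetic mean is the default reading and not explicit text. It is still the natural reading, since the geometric alternative is spelled out for immunoglobulins and not here.

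A reader might also infer that the plan hides a loss of desensitization. The documents do not support that. SAP 9.1.1 gives exit response rates with exact intervals and counts at every highest tolerated dose. If the reference is ARC003 exit, 9.1.2 also shows MTD at both time points. In the 20%/10% example, mean MTD falls by 0.2 × 300 − 0.1 × 300 = 30 mg and the share tolerating 600 mg falls by 10 percentage points. What remains is that these are marginal summaries. The exit rates must be set against a baseline shown elsewhere: ARC003 Exit MTD appears in SAP 8.3 for the Safety population, while challenge summaries use completers (SAP 9.1). No count of who lost, kept or gained a step is described.

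Protocol 7.8.3 does compare each subject with the previous challenge, but as a cohort stopping rule. A move from 600 to 300 mg (1043 to 443 mg cumulative) is not a failure under it, so it would not register this pattern.

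Finally, 0.3 mg can be defended. SAP 7.3 recognises challenges that begin at 1 mg, and 0.3 mg is about half a log below that. A reader might infer that the constant is arbitrary because ARC004 challenges begin at 3 mg, but the reference is an ARC003 challenge whose schedule is not in these documents.

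**Conclusion.** The point holds in a limited form. SAP 9.1.2 leaves the statistic unnamed, and the default gives a summary in which one-step gains outweigh one-step losses on a scale that the SAP itself treats as roughly logarithmic. Under the ARC003 Exit reference, the illustrated net loss appears as 1.00 on both mean and median against a geometric mean of 0.93, or 0.87 in the stronger 50-subject pattern. The size depends on the steps involved (break-even 1.0 to 2.5 losers per gainer) and, for the median at 2:1, on unchanged subjects outnumbering gainers.

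Three stronger readings should not be drawn. The masking does not hold whichever baseline is used; it needs the ARC003 Exit reference. The 0.3 mg value does not cause it; that value is a separate sensitivity of the arithmetic mean when it falls at the reference challenge. Nor is the arithmetic mean invalid: it answers a different question and may be shown as well. With no formal comparisons planned (SAP 6.4) and other challenge summaries available, this is a worthwhile clarification of a secondary endpoint, not a threat to the study's conclusions.

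**What to change.** In SAP 9.1.2:

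1. State the reference challenge for MTD fold change, in agreement with SAP 7.5 and Section 11, and replace the word *screening* accordingly.
2. Report the geometric mean fold change, computed on log MTD, with a 95% CI per group/cohort, descriptive only as in SAP 6.5. The arithmetic mean may stay beside it.
3. Add the number and percent of subjects whose MTD is lower than, the same as, or higher than at the ARC003 Exit DBPCFC. This also makes a complete loss visible without relying on the assigned value.
4. Keep 0.3 mg if its rationale, half a log below a 1 mg first dose, is written down.

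No new data are needed. The cost is SAP wording and a few lines of code. The headline fold increase will be smaller, because a geometric mean cannot exceed the arithmetic mean of the same ratios.
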